11.3 Statistical criteria of termination of the investigation

Due to the nature of the study, statistical criteria of termination of the investigation are not planned.

11.4 Planned Analyses

The primary variable for this assessment is the ability to detect retinal morphological changes with High-Res-OCT in comparison to conventional ophthalmic imaging methods such as OCT, color fundus photography and fluorescein angiography.

To prove the null hypothesis, hypothesis testing will be done with a one-sided 95% confidence interval to exclude a difference in favour of conventional imaging. The results will be displayed using a receiver operating characteristic (ROC) curve and a Precision-Recall (PR) curve. The ROC curve is created by plotting the true positive rate (TPR) against the false positive rate (FPR) at various threshold settings, the PR curve by plotting precision against recall.

Moreover, subgroup analysis will be performed to differentiate different disease entities using non-parametric test with a significance level of 0.05.

Descriptive analyses will evaluate demographic data as well as visual acuity data separately for each group of patients.

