Control intervention (if applicable):	Conventional ophthalmic imaging including optical coherence tomography, fluorescein angiography and color fundus photography.

Number of subjects with rationale:
	
550 subjects
 
Healthy subjects: 100
 
Subgroup analysis will be performed with patients suffering from the following eye diseases:
 
Diabetic retinopathy; approximately 50 patients
 
Artery and vein occlusion; approximately 50 patients
 
Glaucoma; approximately 50 patients
 
Optic nerve neuropathy; approximately 50 patients
 
Hereditary retinal diseases; approximately 50 patients
 
Retinal detachment; approximately 50 patients
 
Age related macular degeneration; approximately 50 patients
 
Retinal changes from arterial hypertension; approximately 50 patients
 
Uveitis ; approximately 50 patients
 
The primary variable for this assessment is the ability to detect the presence of retinal structural abnormalities with High-Res-OCT in comparison to conventional ophthalmic imaging methods, mainly SD-OCT. This will result in a binary outcome. Assuming that the accuracy of each of these conventional imaging modalities separately is 90%, and there is truly no difference between the conventional imaging and High-Res-OCT (null hypothesis), then 550 patients are required to be 90% sure that the upper limit of a one-sided 95% confidence interval (or equivalently a 90% two-sided confidence interval) will exclude a difference in favour of the conventional imaging of more than 10%¹⁶. The results will be displayed using a receiver operating characteristic (ROC), or ROC curve. The curve is created by plotting the true positive rate (TPR) against the false positive rate (FPR) at various threshold settings. Here the required total sample size for estimating sensitivity (presence of the pathological changes within the scans) with respect to marginal error (0.03), sensitivity (90%) and the prevalence (0.9) of disease in target population would be approximately 550 subjects¹⁷.
 
Subgroup analysis will be performed with patients suffering from diabetic retinopathy, artery and vein occlusion, glaucoma, optic nerve neuropathy, hereditary retinal diseases, retinal detachment, age related macular degeneration, retinal changes from arterial hypertension and uveitis. In order to compare these groups with conventional imaging and controlling for some degree of variation due to age, we estimate a group size of approximately 50 patients and 100 healthy subjects.

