
Duration of the investigation:
	
Last participant processed and finishing the study : 30.11.2023

Investigation schedule:
	
31.October 2021
 
30. November 2023

Investigator(s):	
[name]. [name] [name]. [name] [name]. [name] [name] PhD. [name] [name] [name] [name] [name]
 
Universitätsklinik für Augenheilkunde Inselspital [name] Telefon [name]

Investigational Site(s):	
Single center study at Universitätsklinik für Augenheilkunde Inselspital, Bern

Statistical considerations:	
The primary variable for this assessment is the ability to detect retinal morphological changes with High-Res-OCT in comparison to conventional ophthalmic imaging methods such as OCT, color fundus photography and fluorescein angiography. This will result in a binary outcome. Assuming that the accuracy of each of these conventional imaging modalities separately is 90%, and there is truly no difference between the conventional imaging and High-Res-OCT, then 550 patients are required to be 90% sure that the upper limit of a one-sided 95% confidence interval (or equivalently a 90% two-sided confidence interval) will exclude a difference in favour of the conventional imaging of more than 10% ^{16,17}.
 
Subgroup analysis will be performed to differentiate different disease entities using non-parametric test with a significance level of 0.05.
 
Descriptive analyses will evaluate demographic data as well as visual acuity data separately for each group of patients.
 
Subgroup analysis will be performed with patients suffering from diabetic retinopathy, artery and vein occlusion, optic nerve neuropathy, glaucoma, retinal detachment, age related macular degeneration, retinal changes from arterial hypertension and uveitis. In order to compare these groups with conventional imaging and controlling for some degree of variation due to age, we estimate a group size of approximately 50 patients and 100 healthy subjects.

Compliance statement:	
This investigation will be conducted in compliance with the CIP, the current version of the Declaration of Helsinki, ISO14155, ICH-GCP (as far as applicable) as well as all national legal and regulatory requirements.

ABBREVIATIONS

Provide a list of abbreviations used in the CIP – to be completed/adapted

AE	Adverse Event
ADE	Adverse Device Effect
ASADE	Anticipated Serious Adverse Device Effect
ASR	Annual Safety Report
CEC	Competent Ethics Committee

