11. STATISTICAL METHODS

11.1 Hypothesis

The primary variable in this study is the ability to detect pathological changes in the retina/optic nerve in comparison to conventional imaging modalities such as SD-OCT, color fundus photography and fluorescein angiography.

Null hypothesis: there is no difference in detecting pathological changes in the retina/optic nerve between conventional imaging and High-Resolution OCT

Alternative hypothesis: there is a difference in detecting pathological changes in the retina/optic nerve between conventional imaging and High-Resolution OCT

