11.2 Determination of Sample Size

The primary variable for this assessment is the ability to detect the presence of retinal structural abnormalities with High-Res-OCT in comparison to conventional ophthalmic imaging methods, mainly SD-OCT. This will result in a binary outcome. Assuming that the accuracy of each of these conventional imaging modalities separately is 90%, and there is truly no difference between the conventional imaging and High-Res-OCT (null hypothesis), then 550 patients are required to be 90% certain that the upper limit of a one-sided 95% confidence interval (or equivalently a 90% two-sided confidence interval) will exclude a difference in favor of the conventional imaging of more than 10%¹⁶.

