11.4.2 Primary Analysis

The results will be displayed using a receiver operating characteristic (ROC), or ROC curve. The curve is created by plotting the true positive rate (TPR) against the false positive rate (FPR) at various threshold settings. Here the required total sample size for estimating sensitivity (presence of the pathological changes within the scans) with respect to marginal error (0.03), sensitivity (90%) and the prevalence (0.9) of disease in target population would be approximately 550 subjects¹⁷. Depending on the results, precision and recall (PR) curves are also going to be computed, which are useful in case of distribution imbalance between two classes of a binary model, specifically if the true negative values are high, the latter not being taken into account in the calculation³⁰. Precision (Y-axis) is referred as the positive predictive value and recall (X-axis) as sensitivity. A high precision value means that the tested classifier/device provides accurate results, while high recall indicates that the majority of all positive samples were detected. The possible AUC value ranges from 0.5 (discriminative performance equal to chance) to 1.00 (perfect discriminative performance). The primary analysis will be done using

Python 3 and its open-source package Scikit-learn v0.20.3.

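### Sections 11.1 and 11.4 set out to prove a null of no difference with no limit, while 11.2 and the synopsis size a 10-point non-inferiority claim

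*Combined protocol and SAP*

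**What the plan says.** All places are in the combined protocol and SAP.

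- **11.1 Hypothesis:** "Null hypothesis: there is no difference in detecting pathological changes in the retina/optic nerve between conventional imaging and High-Resolution OCT". And: "Alternative hypothesis: there is a difference in detecting pathological changes in the retina/optic nerve between conventional imaging and High-Resolution OCT". There is no direction and no limit.
- **11.4 Planned Analyses:** "To prove the null hypothesis, hypothesis testing will be done with a one-sided 95% confidence interval to exclude a difference". The sentence ends by giving the direction (in favour of conventional imaging) but no size.
- **11.2 Determination of Sample Size:** the calculation takes 90% accuracy for conventional imaging and reads: "there is truly no difference between the conventional imaging and High-Res-OCT (null hypothesis), then 550 patients are required to be 90% certain". Success is judged on the upper end of a one-sided 95% interval, which "will exclude a difference in favor of the conventional imaging of more than 10" per cent.
- **Synopsis, number of subjects:** the same, with "there is truly no difference between the conventional imaging and High-Res-OCT (null hypothesis), then 550 patients are required to be 90% sure" and "will exclude a difference in favour of the conventional imaging of more than 10" per cent. The synopsis row on statistical considerations repeats the 10% limit but does not call zero difference the null hypothesis.
- **11.4.2 Primary Analysis:** "The results will be displayed using a receiver operating characteristic (ROC), or ROC curve". Precision-recall curves may be added. The 10-point limit does not appear.
- **5.1 Primary Outcome:** asks whether High-Res-OCT is at least as good as conventional imaging, which is a one-directional aim.

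**The concern.** The hypotheses, the test and the sample size should describe one question, and here they do not. Section 11.1 poses a test of equality. Section 11.2 sizes a non-inferiority claim with a 10-point limit. Section 11.4 uses the interval from 11.2 but ties it to the null of 11.1 and leaves out the limit.

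What is at stake is the conclusion that may be drawn. Under 11.4 as written, a favourable interval could be reported as proof that the devices do not differ, which no interval can show. Section 4.1 hopes to make other imaging, including fluorescein angiography, unnecessary, so the gap between equal and not worse by 10 points or more matters to readers. Section 11.4.5 also allows the analysis to be adapted while it is under way, provided that deviations are described and justified. That is a further reason to have the primary rule written down beforehand.

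**Working it through.** **Inputs.** From 11.2: accuracy 90%, true difference 0, limit 10 points, one-sided 95% interval, 90% power, N = 550. Pairing follows from 9.1, where subjects due for routine imaging also have High-Res-OCT. The documents do not give the share of subjects on whom the two methods disagree (discordance, q). I assume 5-20%. Independent errors at 90% accuracy would give 2 × 0.9 × 0.1 = 18%. Let D be conventional imaging minus High-Res-OCT.

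**1. The plan's own figure.** The inputs of 11.2 do not return 550.
- Two independent groups: n = (1.645 + 1.282)² × 2 × 0.9 × 0.1 / 0.10² gives 155 per group, 310 in total.
- Paired: n = (1.645 + 1.282)² × q / 0.10² gives 43 subjects at q = 5% and 172 at q = 20%.

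This is a separate matter. It is noted here only because 550 cannot be used to work out which hypothesis was meant.

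**2. Which null fits the sizing.** An interval whose upper limit for D must fall below 10 points tests H0: D ≥ 10 points against H1: D < 10 points. The state D = 0, at which 11.2 computes its 90%, lies inside H1. The null in 11.1 is D = 0, so what 11.1 calls the null is a point in the alternative of the design that was sized.

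**3. What 11.4 does if read literally.** With no limit given, excluding a difference in favour of conventional imaging means an upper limit for D below 0. At true equality the probability is Φ(-1.645) = 5%, which is alpha by construction. Success would show that High-Res-OCT is better, which is evidence against the null that 11.4 wants to prove. For 90% power under this reading, High-Res-OCT would have to be truly better by (1.645 + 1.282) × √(q/550):
- q = 5%: 2.8 points
- q = 10%: 3.9 points
- q = 18%: 5.3 points

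**4. The same interval with the 10-point limit.** At D = 0 the power is Φ(0.10/√(q/550) - 1.645).
- q = 5%: Φ(10.49 - 1.645), effectively 100%
- q = 10%: Φ(7.42 - 1.645), over 99.9%
- q = 18%: Φ(5.53 - 1.645), over 99.9%
- q = 20%: Φ(5.24 - 1.645) = 99.98%

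If 550 were instead split into two groups of 275, Φ(0.10/√(0.18/275) - 1.645) = 98.8%.

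**5. The label.** Section 11.2 and the synopsis row on number of subjects attach the term null hypothesis to the planning assumption of zero difference. Section 11.1 is a valid equality null in itself, but the wrong one for this design. Section 11.4 takes over that null and treats it as provable.

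**The case against.** The strongest reply is that the intent can be recovered. Section 5.1 points to non-inferiority, 11.2 and 11.4 share the same one-sided interval and direction, the 10% limit is stated three times, and no competing value appears anywhere. Section 11.4.2 sits under 11.4, so the interval applies to it too. This stands, and it is why the repair is cheap. It does not remove the conflict: 11.1 states a different test, and 11.4 states a conclusion that the interval cannot give.

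Three stronger readings are tempting, and the documents do not support them.

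- A reader might infer that the trial could reach contradictory primary results, with equality rejected and the 10-point criterion met in the same data. No two-sided primary test is planned; the only inferential rule for the primary comparison is the one-sided interval. The two results are also compatible, since a true 3-point deficit is both a difference and less than 10 points. They could still occur together after the fix.
- A reader might infer that a non-significant test would be reported as proof of equality. Section 11.4 ties the proof to an interval that excludes a deficit, not to a failure to reject.
- A reader might infer that the term null hypothesis is mislabelled wherever it occurs. Only 11.2 and one synopsis row put it on a planning assumption.

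**Conclusion.** The point holds as a mismatch between the stated hypotheses, the stated test and the sized claim. The wording of 11.1 and 11.4 is wrong for the design in 11.2 and should be corrected before the data are analysed.

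In size, the missing limit separates a rule met about 5% of the time at true equality from one met in over 99.9%. The second figure assumes that all 550 subjects contribute a paired comparison on the single measure that 11.2 sizes, with discordance of 5-20%. The 5% is not a forecast of how the trial will perform: it follows from the level of the interval, and the literal reading conflicts with the aim of 11.4 itself. It shows only that the limit cannot be left unstated.

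The over-99.9% figure does not carry over to sensitivity and specificity taken separately, which rest on fewer subjects. Whether to restrict the comparator to SD-OCT, and whether accuracy or sensitivity and specificity should be primary, are separate questions (4.2, 5.1, 9.1, 9.2.1, 11.5). This point does not settle them.

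**What to change.** - **11.1:** replace both hypotheses with: *H0: conventional imaging minus High-Res-OCT ≥ 10 percentage points; H1: < 10 percentage points.* Use the same measure and the same comparator here as in 11.2 and 11.4.
- **11.4, and by reference 11.4.2:** replace the sentence on proving the null with: *Non-inferiority is claimed only if the upper limit of the one-sided 95% confidence interval for the within-subject (paired) difference, conventional imaging minus High-Res-OCT, is below 10 percentage points; equality is not claimed.*
- **11.2 and the synopsis row on number of subjects:** change the bracketed label on zero difference to *planning assumption*.

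The cost is rewording only, with no extra subjects or data. The sponsor gives up the claim of no difference: the conclusion is limited to not worse by 10 points or more.

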11.4.1 Datasets to be analysed, analysis populations

Descriptive analyses will evaluate demographic data, such as age, gender, as well as visual acuity data separately for each group of patients. No additional analyses will be performed. However, if the data are significant, a longitudinal study will be planned and submitted.

11.4.2 Primary Analysis

The results will be displayed using a receiver operating characteristic (ROC), or ROC curve. The curve is created by plotting the true positive rate (TPR) against the false positive rate (FPR) at various threshold settings. Here the required total sample size for estimating sensitivity (presence of the pathological changes within the scans) with respect to marginal error (0.03), sensitivity (90%) and the prevalence (0.9) of disease in target population would be approximately 550 subjects¹⁷. Depending on the results, precision and recall (PR) curves are also going to be computed, which are useful in case of distribution imbalance between two classes of a binary model, specifically if the true negative values are high, the latter not being taken into account in the calculation³⁰. Precision (Y-axis) is referred as the positive predictive value and recall (X-axis) as sensitivity. A high precision value means that the tested classifier/device provides accurate results, while high recall indicates that the majority of all positive samples were detected. The possible AUC value ranges from 0.5 (discriminative performance equal to chance) to 1.00 (perfect discriminative performance). The primary analysis will be done using

Python 3 and its open-source package Scikit-learn v0.20.3.

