4.2 Primary Objective

The primary objective of this study is to evaluate the sensitivity and specificity to diagnose retinal morphological abnormalities with High-Resolution OCT compared to conventional imaging methods, such as SD-OCT, fluorescein angiography. The main parameters, which will be assessed are the presence of morphological abnormalities (such as but not limited to intraretinal or subretinal fluid, epiretinal membrane, substance defect, drusen, hyperreflective foci, atrophy, neovascularization, optic nerve, swelling, choroid abnormalities, scars, ischemia) within the macula and optic nerve head. The incidence (binary) and diagnostic accuracy of these morphological abnormalities will be assessed in High-Res-OCT and compared to conventional imaging methods such as SD-OCT.

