5. CLINICAL INVESTIGATION OUTCOMES

5.1 Primary Outcome

The primary outcome as measured on the individual patient-level is whether High-Resolution OCT has a similar or higher specificity and sensitivity to detect pathological changes in the retina/optic nerve as conventional imaging methods, such as SD-OCT, color fundus photography and fluorescein angiography. This will result in a binary outcome. Pathological morphological changes includes but are not limited to, intraretinal or subretinal fluid, epiretinal membrane, substance defect, drusen, hyperreflective foci, atrophy, neovascularization, optic nerve swelling, choroid abnormalities, scars, ischemia. Additionally, study participants will be asked to consent to prospective collection of clinical and demographic data, to correlate findings of High-Resolution OCT imaging to subsequent clinical course.

Ophthalmic diseases include, but are not limited to:

- Retinal vascular diseases
- Retinal detachment
- Hereditary retinal diseases/dystrophies
- Glaucoma
- Optic nerve neuropathy
- Inflammatory/infectious retinal diseases

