9.2.1 Assessment of primary outcome

The sensitivity and specificity of the High-Resolution OCT to diagnose the presence/absence of pathological changes in the retina/optic nerve in comparison to conventional imaging modalities will be assessed as a primary outcome. The following pathological changes will be assessed: intraretinal or subretinal fluid, pigment epithelial detachment, epiretinal membrane, substance defect, drusen, hyperreflective foci, atrophy, neovascularization, choroid abnormalities, scars, optic nerve swelling and ischemia. For each of these pathological changes a binary outcome will result. Additionally, study participants will be asked to consent to prospective collection of clinical and demographic data, to correlate findings of High-Res-OCT imaging to subsequent clinical course.

There is no need to be in a particular posture before the examination in order to obtain high quality images. The participants will be in a sitting position during the examination during approximately 30-60 seconds per eye. In case the measurement needs to be repeated, no waiting period will be necessary. A repeated measurement needs to be recorded in the CRF.

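### The primary decision rule names no measure, so specificity, half of the primary outcome, has no success criterion; the planned ROC curve also cannot be drawn from yes/no reads

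*Combined protocol and SAP*

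**What the plan says.** Section 4.2 sets the primary objective: to "evaluate the sensitivity and specificity to diagnose retinal morphological abnormalities with High-Resolution OCT compared to conventional imaging methods". Section 5.1 puts it as a question about both measures: "The primary outcome as measured on the individual patient-level is whether High-Resolution OCT has a similar or higher specificity and sensitivity". Section 9.2.1 lists the changes to be read and adds: "For each of these pathological changes a binary outcome will result".

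The decision rule is in 11.4: "hypothesis testing will be done with a one-sided 95% confidence interval to exclude a difference in favour of conventional imaging". That sentence gives neither a measure nor a margin. The margin is in the sample-size text. Section 11.2 describes the comparison as "in comparison to conventional ophthalmic imaging methods, mainly SD-OCT" and starts its calculation with "Assuming that the accuracy of each of these conventional imaging modalities separately is 90" per cent. The synopsis carries the same calculation and concludes that the upper limit "will exclude a difference in favour of the conventional imaging of more than 10" per cent.

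Section 11.4.2, headed as the primary analysis, contains no test, estimator or success criterion. It offers a ROC display ("The curve is created by plotting the true positive rate (TPR) against the false positive rate (FPR) at various threshold settings"), a precision-based sample size for sensitivity, optional precision-recall curves and the possible range of an AUC. Section 11.1 states a plain no-difference null against a difference, and 11.4 speaks of proving that null.

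**The concern.** The trial asks whether High-Res-OCT is at least comparable on two measures, but its one formal rule is tied by name to neither. No section gives specificity an assumed value, a margin, a test or a sample size. The trial could therefore report that sensitivity and specificity are both at least similar without having tested specificity. That matters here because 4.1 hopes to make other imaging unnecessary, and a modality that shows more detail could also produce more positive reads in eyes without disease.

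The ROC problem is separate and smaller. A ROC curve needs a graded score, and none is defined for the primary reads.

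**Working it through.** **1. The plan's own figure.** Inputs from 11.2: 90% in both modalities, true difference 0, margin 0.10, one-sided alpha 0.05, power 90%. (1.645 + 1.282)² = 8.56.
- Two independent groups: 2 × 0.9 × 0.1 × 8.56 / 0.10² = 154.1, so 155 per group or 310 in total.
- Paired reads: ψ × 8.56 / 0.10², where ψ is the share of subjects whose two reads disagree. This gives 43, 86 and 155 subjects at ψ = 0.05, 0.10 and 0.18.
- Precision route in 11.4.2: 1.96² × 0.9 × 0.1 / 0.03² = 384.1 diseased, and 384.1 / 0.9 = 427 in total.

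None of these gives 550. That is a different matter, and nothing below depends on it. What matters here is that neither route uses specificity.

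**2. What each measure receives.**

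| Measure | Primary outcome? | Assumed value | Margin |
|---|---|---|---|
| Sensitivity | yes (4.2, 5.1, 9.2.1) | 90%, ±0.03 (11.4.2) | none by name |
| Specificity | yes (4.2, 5.1, 9.2.1) | none | none |
| Accuracy | mentioned in 4.2, not the 5.1 outcome | 90% (11.2, synopsis) | 10 points, by context |

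**3. If the rule is on overall accuracy.** Take the patient-level read of any pathological change, and let the 450 patients and 100 healthy subjects of 6.1 stand in for true status. The accuracy difference is (450/550) × sensitivity difference + (100/550) × specificity difference, that is, weights of 0.818 and 0.182. With equal sensitivity, a 20-point specificity loss moves accuracy by 0.20 × 100/550 = 0.036.

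**4. Largest observed specificity loss L that still passes.** Solve d + 1.645 × √((ψ − d²)/550) = 0.10, with d = 100L/550 and ψ = (450ψ_P + 100L)/550. Here ψ_P is the discordance among patients, and healthy discordance is the least that the loss allows. The documents give no discordance, so ψ_P is an assumption.
- ψ_P = 0.05: L = 0.421
- ψ_P = 0.10: L = 0.401
- ψ_P = 0.18: L = 0.373

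Check at 0.18: d = 0.0678, ψ = 0.2151, standard error 0.0196, upper limit 0.0678 + 1.645 × 0.0196 = 0.100.

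**5. Simulated pass rates at a true 20-point loss** (200,000 trials per setting, same assumptions). The accuracy rule passes in over 99.9%, over 99% and about 97% of trials at ψ_P = 0.05, 0.10 and 0.18. A rule on specificity in the 100 healthy subjects, with the same margin, passes in under 0.1%.

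**6. Where this does not apply.** Suppose a single change is present in 50 of 550 subjects (an assumption). The same 20-point loss then moves accuracy by 0.20 × 500/550 = 0.182, and the accuracy rule passed in no simulated trial.

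**7. If accuracy means sensitivity.** Steps 3 to 5 fall away. Specificity then has no rule, so there is nothing to compute.

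**8. ROC.** A yes/no read gives the points (0, 0), (1 − specificity, sensitivity) and (1, 1). The area under the two joining lines is (sensitivity + specificity)/2. At 0.90 and 0.90, scikit-learn returns (0, 0), (0.1, 0.9) and (1, 1), with area 0.90. The area adds nothing to the two numbers.

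**9. Power if each measure has its own rule.** Power = Φ(0.10/√(ψ/n) − 1.645), true difference 0.

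| n | ψ = 0.05 | ψ = 0.10 | ψ = 0.18 |
|---|---|---|---|
| 100 (specificity) | 0.998 | 0.935 | 0.762 |
| 450 (sensitivity) | >0.999 | >0.999 | >0.999 |

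**The case against.** The strongest reply is that accuracy is loose wording. Section 11.4.2 sizes on a sensitivity of 90%, the same figure, and the plan also uses diagnostic accuracy as a general term. A reader might infer that the rule is certainly on overall accuracy and that the trial would therefore let a large specificity loss through. The documents do not support that certainty, because 11.4 names no measure. What stands is the gap, which is present under either reading.

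The size also depends on the read. Section 9.2.1 yields a result for each change, and for a change that is mostly absent the negatives dominate and the accuracy rule becomes strict on specificity (step 6). This objection stands, and the figures are limited accordingly.

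Two other stronger readings should be set aside. The prevalence of 0.9 in 11.4.2 might suggest only 55 non-diseased subjects and still larger tolerated losses, but that value is an input to a precision formula, while 6.1 plans 100 healthy subjects. The ROC defect might be taken to invalidate the primary analysis, but the curve is a display and no AUC test is planned. Both rates could still be shown, so a loss of specificity would be visible though not formally tested.

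**Conclusion.** The concern holds in this form: the primary rule names no measure or margin, its margin follows an assumption about accuracy, and specificity has no criterion anywhere in the plan.

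The figures apply only to overall accuracy of the patient-level any-change read, with the 450:100 split standing in for true status, equal sensitivity and assumed patient discordance of 0.05 to 0.18. Within those limits, observed specificity losses of up to about 42 to 37 points still pass.

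A reader might also infer that the trial is underpowered for specificity. That goes too far: power with 100 true negatives exceeds the stated 90% at discordance 0.05 and 0.10 and falls below it only towards the upper end of the range.

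The ROC point is correct but secondary. The plan should be changed, and the change is mainly one of text.

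**What to change.** - **11.4.2:** state that the primary analysis is the within-participant difference, SD-OCT minus High-Res-OCT, in sensitivity and separately in specificity, for the patient-level read of any pathological change, in participants with both scans. Each difference has the one-sided 95% CI of 11.4, and both upper limits must lie below the 10 points of 11.2. SD-OCT is named because 11.2 makes it the main comparator. Report single changes and the other comparators separately.
- **11.1 and 11.4:** reword to match. The null is that High-Res-OCT is worse by 10 points or more on sensitivity or on specificity. Remove the statement about proving the null.
- **Reference standard:** say what defines true status and whether it depends on the SD-OCT read. Patients enter because they need conventional imaging (7.1, 9.1), so the diagnosis recorded under 12.1.2 may rest on SD-OCT. If it does, state this as a limit on the comparison.
- **Display:** replace the multi-threshold ROC and precision-recall curves and the AUC with each modality's sensitivity and specificity, with CIs.
- **Power:** restate it for both measures, with the discordance range: about 99.8%, 93.5% and 76% for specificity at 0.05, 0.10 and 0.18, and above 99% for sensitivity.

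**Cost.** No extra imaging or enrolment is needed, and no alpha split, because both differences must pass. An adjudicated reference read, if chosen, would need one yes/no field. Holding both measures to the same 10 points is a choice that the sponsor must own. Specificity power may fall below 90%. Section 9.1 lets the routine modality differ between subjects, so those without SD-OCT leave the paired set, and the documents do not give their number. If 80% had SD-OCT (an assumption: 360 patients, 80 healthy), specificity power would be about 99%, 88% and 68% over the same discordance range, with sensitivity still above 99%.
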